## Protocol Summary

Full Title:	A PHASE II STUDY OF DARATUMUMAB, CLARITHROMYCIN, POMALIDOMIDE AND DEXAMETHASONE (D-ClaPd) IN MULTIPLE MYELOMA PATIENTS PREVIOUSLY EXPOSED TO DARATUMUMAB
Short Title:	D-ClaPd IN REL/REF MULTIPLE MYELOMA
Clinical Phase:	2
Principal Investigator:	[name] [name]
Study Description:	This single-arm phase 2 study will test the hypothesis that in patients with previous daratumumab exposure, daratumumab in combination with ClaPd will yield higher $\geq$ VGPR rates in historical pomalidomide/dexamethasone.
Sample Size:	N= 40
Enrollment:	This study will enroll 40 subjects and screen up to 44 subjects.
Study Population:	Patients will be over 18 years of age with relapsed/refractory multiple myeloma. Patients who have received 1 or more prior lines of therapy which must include daratumumab and may include ASCT are eligible. The patient must have received both an IMiD and PI in prior lines. Prior pomalidomide exposure in 1 or more previous lines of therapy allowed if PR or better achieved. No disease progression may have occurred within 60 days of receiving pomalidomide. Patient may be daratumumab refractory (i.e less than a PR) achieved on prior daratumumab-based therapy or have exhibited progression within 60 days of receiving daratumumab.
Study Design:	This is a single-center single-arm phase 2 study in which 40 patients will receive daratumumab in combination with clarithromycin/pomalidomide/dexamethasone until PD or unacceptable toxicity, whichever comes first. Patients will be treated for 8 cycles of therapy with continuation of maintenance daratumumab/pomalidomide if evidence of PR or better.

## Facilities Enrolling

**Participants:**

Weill Cornell Medical College-NewYork Presbyterian Hospital (WCMC/NYPH), Brooklyn Methodist Hospital (BMH), and NewYork-Presbyterian Queens (NYPQ)

Participant Duration:	Time it will take for each individual participant to complete all participant visits in the induction phase is 8 months. Patients who complete all 32 cycles of treatment for the entire study, if have not progressed or started new treatment, will be followed with disease evaluations every 90 days (+/- 30 days) until confirmed disease progression or for total duration of 24 months from last EOT visit, whichever comes first, and for survival for up to 10 years from date of enrollment or until death.
Study Agent/Device Name	
Intervention Description:	
Induction Phase (Cycles 1-8, q28 day cycles):
 
 
• Daratumumab 1800 mg SC weekly x 8 wks, 1800 mg SC q2wk days 1 and 15 (cycles 3-6) 1800 mg SC q4wk day 1 (cycles 7-8)
 
• Clarithromycin 500mg PO bid continuous until VGPR or 8 cycles, whichever occurs first
 
• Pomalidomide 4 mg PO days 1-21
 
• Dexamethasone 20 mg IV as premed days 1 and 8 (cycle 1); 20 mg PO days 2 and 9 (cycle 1); 40 mg PO as premed days 15 and 22 (cycle 1); 40 mg PO qwk (cycles 2-6); 20 mg PO qwk (cycles 7-8)
 
 
Maintenance Phase (Cycle 9+): up to 24 months q28 day cycles
 
 
• Daratumumab 1800 mg SC day 1
 
• Pomalidomide 4 mg PO days 1-21
 
• Dexamethasone 20 mg PO qwk
 

Primary Objective:	PRIMARY: To determine best response rate within 8 cycles of induction therapy.
Secondary Objectives:	SECONDARY: To determine median PFS and OS, time to response (TTR), time to progression (TTP), response duration, time to next therapy (TTNT), time to $\geq$ VGPR, ORR, CR or better rate, MRD negativity rate after 8 and 32 months, AEs in induction and maintenance phases, clinical response in high-risk groups.
Exploratory Objectives:	Assessment of MRD by multiparameter flow cytometry (MFC), FISH, NGS, PET/MRI imaging studies at best response. MFC-based tests of BM aspirates of both CD138-isolated clonal plasma cells and immune cells from marrow and tissue will be studied for various immune-based and daratumumab-based markers; dose-intensity analyses (mean relative dose intensity of dexamethasone); QoL assessments.
Endpoints:	Primary Endpoint:

The primary endpoint is the  $\geq$  VGPR response proportion; A 95% confidence interval will be estimated for the  $\geq$  VGPR response proportion via binomial proportions.

*Secondary endpoints:* include median PFS, OS, time to response and progression, DoR, TTNT, ORR, VGPR rate, CR or better rate, and MRD negativity rate. Median PFS/OS, including survival curves, will be estimated using Kaplan-Meier methodology. Greenwood's formula will be used to calculate 95% confidence intervals for the Kaplan-Meier survival estimates.

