### SCHEDULE OF STUDY PROCEDURES

Screening Phase  Day-28 to 0		Treatment	End of Treatm	Post-Treatment Observation Phase
		(Cycle is 28 days) +/- 3 days for Cycle 1 and 2, +/- 7 days for Cycles 3-30	At 1 year (+/- 7 days) & 90 days after last dose of study drug (+/-7 days)	Each cycle is 90 days, +/- 30 days for 24 months or until progression
Informed consent a	X			
Inclusion/exclusion criteria review	X			
Demography/Medical history	X			
Physical Exam	X	X b (every cycle)	X	
Vital signs c	X	X d (every cycle)	X	
Weight	X	X (every cycle)	X	
ECOG status	X	X (every cycle)	X	
ECG	X			
Echocardiogram	X		X	
Pulmonary function testing e	X e		X e	
Chest x-ray f				
NYHA classification	X	X (cycle 1 only)	X	
Patient Diary g	X	X (every cycle)	X	
Concomitant medications	Continuous from time of ICF until 30 days of last treatment			
Adverse events	Continuous from time of ICF until 30 days of last treatment			
Study Drug Administration				
Daratumumab 1800 mg SC dosing h		Daratumumab 1800 mg SC on Days 1, 8, 15, and 22 of Cycles 1 and 2 (weekly dosing), on Days 1 and 15 of Cycles 3 to 6 (every 2 weeks dosing), and on Day 1 of Cycle 7 and subsequent cycles (every 4 weeks dosing)		

Clarithromycin		500 mg PO bid continuous days 1-28 of cycles 1-8 only		
Pomalidomide		Pomalidomide 4 mg PO days 1-21		

Dexamethasone		Dexamethasone (Cycle 1 D1 & 8): 20 mg IV Cycle 1 D2 & D9: 20mg PO Cycle 1 D15 & D22: 40mg PO Cycles 2- 6: 40 mg PO qwk Cycles 7- 8: 20mg PO qwk Cycle 9+: 20mg PO qwk		
Prophylactic Medications				
Varicella Zoster Prophylaxis		Valacyclovir 500mg PO qd (or equivalent, renally dosed-adjusted)		
Gastrointestinal Prophylaxis		Pantoprazole 40 mg PO daily, or other		
Laboratory Assessments				
Pregnancy test i	X	X	X	
Blood typing/indirect antiglobulin test	X			
Hematology (CBC) with differential	X	On Days 1, 8, 15, and 22 for Cycles 1 and 2; On Days 1 and 15 for Cycles 3 through 6; D1 from Cycle 7 onward and as clinically indicated	X	
Serum chemistry j	X	On Days 1, 8, 15, and 22 for Cycle 1-2, Day 1, 15 for cycles 3-6 and day 1 of each subsequent cycle	X	
Hepatitis B and C screening k	X	HBV DNA monitoring q12weeks	X	X i
Disease Assessments				
Serum $\beta$ 2-microglobulin	X			
Serum free light chains	X	X (every cycle)	X	X (every cycle)

SPEP and IFE	X	X (every cycle)	X	X (every cycle)

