#### Cycles 2-6 (28-day cycle)

- Daratumumab 1800 mg SC on days 1, 8, 15, and 22 for Cycle 2 and Daratumumab 1800 mg SC q2wk days 1 & 15 Cycles 3-6
- Clarithromycin 500 mg PO bid continuous days 1-28 (if <VGPR and discontinued if VGPR achieved)
- Pomalidomide 4 mg PO on days 1-21 of 28-day cycle

- Dexamethasone 40 mg PO will be administered as a premedication prior to daratumumab injection weekly for Cycle 2 and biweekly for Cycles 3-6
- Dexamethasone 40 mg PO weekly on non-daratumumab treatment days (Cycles 3-6)

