#### *6.2.1.2 Concomitant Medications*

##### Pre-injection Medications

Administer the following premedications to reduce the risk of reactions to all patients 1-3 hours prior to every SC injection of daratumumab.

- Dexamethasone 20 mg IV or PO. Dexamethasone must be given intravenously prior to the first daratumumab dosing and oral administration may be administered prior to subsequent injections.
- Antipyretic (oral acetaminophen 650 mg to 1000 mg)
- Antihistamine (oral or intravenous diphenhydramine 25-50 mg IV)
- Leukotriene receptor antagonist (oral montelukast 10 mg)
- If FEV1  $\leq$  80% at baseline, strongly consider administering  $\beta$ 2-adrenergic agonist inhaler (e.g. albuterol)

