**Table 6-4 Dexamethasone Dose Levels**

Dose Level	Dose (mg)
Starting Dose (weekly)	40 mg
-1	20 mg
-2	12 mg
-3	8 mg

**NOTE:** The 20 mg dose of dexamethasone premedication must still be given before the injection on the day of each daratumumab administration regardless of any dexamethasone dose reductions. Therefore, the -2 and -3 dose level weekly dexamethasone dose adjustments only apply to dexamethasone doses on non-daratumumab administration weeks.

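### For patients under 70, the premedication rule in section 6.2.1.2 and the dexamethasone schedule state different doses for 14 of the 18 induction injections of daratumumab

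*Combined protocol and SAP*

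**What the plan says.** **The schedule (patients under 70).** The Intervention Description in the Protocol Summary gives dexamethasone as "40 mg PO as premed days 15 and 22 (cycle 1); 40 mg PO qwk (cycles 2-6"). The Schedule of Study Procedures agrees: "Cycle 1 D15 & D22: 40mg PO Cycles 2- 6: 40 mg PO qwk". The synopsis uses the word premed for 40 mg only on cycle 1 days 15 and 22, and the calendar does not use it at all. The link to daratumumab for the remaining injections comes from two other places:

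- Section 4.1, Cycles 2-6: "Dexamethasone 40 mg PO will be administered as a premedication prior to daratumumab injection weekly for Cycle 2 and biweekly for Cycles 3-6". The cycle 1 text of the same section likewise makes 40 mg the premedication on days 15 and 22.
- Section 6.2.4 repeats the weekly doses and says that dexamethasone falling on a daratumumab day is to be given as the premedication.

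**The premedication rule.** Section 6.2.1.2, Pre-injection Medications, applies to all patients before every subcutaneous injection and lists "Dexamethasone 20 mg IV or PO. Dexamethasone must be given intravenously prior to the first daratumumab dosing". It carries no qualifier by cycle or age.

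**The dose-reduction note.** Under Table 6-4 (section 6.3.5): "The 20 mg dose of dexamethasone premedication must still be given before the injection on the day of each daratumumab administration", whatever reductions have been made. The note then concludes that levels -2 and -3 (12 mg and 8 mg) apply only in weeks without daratumumab.

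**The pointers.** Calendar footnote h, attached to the daratumumab row, and section 6.2.1 both send staff to section 6.2.1.3 for the premedications. The rule is in section 6.2.1.2.

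**The concern.** The schedule and the premedication rule describe the same act, the dexamethasone given before the injection, and put different doses on it. The calendar sends staff from the daratumumab row to the premedication section, while its own dexamethasone row says 40 mg, so staff following the calendar will meet both instructions.

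Dexamethasone is one of the four drugs under test. The trial has a single arm whose rate of VGPR or better is judged against a historical 9% for pomalidomide/dexamethasone, and the randomized phase 2 pomalidomide/dexamethasone study described in section 1.1 used 40 mg per week. If staff resolve the conflict differently, patients receive different weekly steroid doses under one regimen label. The protocol also plans a mean relative dose intensity of dexamethasone (section 3.3.5), which needs an unambiguous planned dose.

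**Working it through.** The documents give no count of injections and no planned total of dexamethasone, so there is no stated figure to reproduce. The check is an enumeration.

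**Inputs**

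- Daratumumab, cycles 1-6 (Protocol Summary): "Daratumumab 1800 mg SC weekly x 8 wks, 1800 mg SC q2wk days 1 and 15 (cycles 3-6"). That is 8 injections in cycles 1-2 and 4 × 2 = 8 in cycles 3-6.
- Daratumumab, cycles 7-8 (Protocol Summary): "1800 mg SC q4wk day 1 (cycles 7-8"). That is 2 injections.
- The Schedule of Study Procedures gives the same pattern: "on Days 1 and 15 of Cycles 3 to 6 (every 2 weeks dosing), and on Day 1 of Cycle 7 and subsequent cycles".
- Dexamethasone doses for patients under 70: sections 4.1 and 6.2.4.
- Premedication dose: section 6.2.1.2, 20 mg before every injection.

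**Step 1. Injections and stated doses**

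| Injection days | Number | Schedule (4.1, 6.2.4) | Rule (6.2.1.2) | Same? |
|---|---|---|---|---|
| Cycle 1, days 1 and 8 | 2 | 20 mg | 20 mg | yes |
| Cycle 1, days 15 and 22 | 2 | 40 mg | 20 mg | no |
| Cycle 2, days 1, 8, 15, 22 | 4 | 40 mg | 20 mg | no |
| Cycles 3-6, days 1 and 15 | 8 | 40 mg | 20 mg | no |
| Cycles 7-8, day 1 | 2 | 20 mg | 20 mg | yes |

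Total injections: 2 + 2 + 4 + 8 + 2 = 18. Injections with two stated doses: 2 + 4 + 8 = 14. Proportion: 14/18 = 78%.

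**Step 2. Scheduled induction total, under 70**

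- Cycle 1: (20 + 20) + (20 + 20) + 40 + 40 = 160 mg
- Cycles 2-6: 5 × 4 × 40 = 800 mg
- Cycles 7-8: 2 × 4 × 20 = 160 mg
- Total: 160 + 800 + 160 = 1120 mg

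**Step 3. Total if section 6.2.1.2 is followed on the 14 days**

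Difference per injection: 40 - 20 = 20 mg. Over 14 injections: 14 × 20 = 280 mg.

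- No remainder given that week (assumption): 1120 - 280 = 840 mg, and 280/1120 = 25% less.
- A 20 mg remainder given on another day of the same week, as cycle 1 does on days 2 and 9: 840 + 14 × 20 = 1120 mg, no change. No passage provides for such a remainder on these 14 days.

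**Step 4. Relative dose intensity**

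With 1120 mg as the planned dose, a patient treated exactly as section 6.2.1.2 says would show 840/1120 = 75% without the remainder and 1120/1120 = 100% with it.

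**Scope.** Sections 4.1 and 6.2.4 halve the dose from age 70, which gives 20 mg on these same 14 injections. The count above is therefore for patients under 70 only.

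**The case against.** The strongest reply is that the regimen is stated once and consistently. The synopsis, calendar, section 4.1 and section 6.2.4 agree on every dose for patients under 70, and Table 6-4 gives 40 mg as the weekly starting dose. Section 6.2.1.2 falls under concomitant medications and lists agents to prevent reactions, so a sensible reader would treat its 20 mg as a minimum that the 40 mg satisfies. On this view only a loosely worded line needs a cross-reference.

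Much of this stands, and it rules out several stronger readings:

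- **That the 20 mg is added to the 40 mg.** A reader might infer a total 25% above plan. Section 6.2.4 makes the dexamethasone given on a daratumumab day the premedication, and section 4.1 counts the day 1 and day 8 premedication within the 40 mg weekly total. The additive reading has no support.
- **That the Table 6-4 note is a second conflicting dose.** Its conclusion bars only the levels below 20 mg in daratumumab weeks, which leaves 40 mg and 20 mg usable there. It reads as a floor during dose reductions.
- **That the route conflicts on cycle 1 day 8.** Section 6.2.1.2 requires the intravenous route before the first dose and merely permits oral dosing afterwards. Intravenous dosing on day 8 meets both texts.
- **That the dose-intensity analysis has no denominator.** The concordant schedule supplies one, 1120 mg. The difficulty is that another section instructs a different dose on most injection days.

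What does not stand is the claim that nothing needs resolving. Section 6.2.1.2 states 20 mg flatly for all patients and every injection. It does not call this a minimum or refer to section 6.2.4, and the floor in the Table 6-4 note is worded for dose reductions.

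**Conclusion.** The point holds. For patients under 70, section 6.2.1.2 and the schedule in sections 4.1 and 6.2.4 state different premedication doses of a study drug on 14 of 18 induction injections. That count follows from the text and needs no assumption.

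The effect on cumulative dose does need one. The scheduled total is 1120 mg. It falls to 840 mg (-25%) only if section 6.2.1.2 is followed on all 14 days and no remainder is given that week. If a remainder is given, the total is unchanged. The corresponding relative dose intensity runs from 75% to 100%.

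A reader might go further and infer that the primary analysis is compromised. The documents do not support that: the endpoint, the 9% and 25% reference rates and the rule of 8 responders in 40 do not depend on this passage, and the dose-intensity analysis is exploratory. What is at stake is uniform delivery of the regimen to which the response rate will be credited. No view is taken here on which dose is right.

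**What to change.** 1. Reconcile section 6.2.1.2 with sections 4.1 and 6.2.4, so that one premedication dose is stated for each injection day and the text says whether the scheduled dose is itself the premedication. The clinical team decides which passage governs.
2. Align the wording of the Table 6-4 note with the result, so that its role during dose reductions is explicit.
3. Correct the cross-reference to section 6.2.1.3 in calendar footnote h and in section 6.2.1.
4. Name the reconciled schedule as the planned dose for the relative dose intensity of dexamethasone in section 3.3.5.

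The cost is a wording amendment. It adds no patients, visits or procedures and does not change the sample size or the primary test.

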### SCHEDULE OF STUDY PROCEDURES

Screening Phase  Day-28 to 0		Treatment	End of Treatm	Post-Treatment Observation Phase
		(Cycle is 28 days) +/- 3 days for Cycle 1 and 2, +/- 7 days for Cycles 3-30	At 1 year (+/- 7 days) & 90 days after last dose of study drug (+/-7 days)	Each cycle is 90 days, +/- 30 days for 24 months or until progression
Informed consent a	X			
Inclusion/exclusion criteria review	X			
Demography/Medical history	X			
Physical Exam	X	X b (every cycle)	X	
Vital signs c	X	X d (every cycle)	X	
Weight	X	X (every cycle)	X	
ECOG status	X	X (every cycle)	X	
ECG	X			
Echocardiogram	X		X	
Pulmonary function testing e	X e		X e	
Chest x-ray f				
NYHA classification	X	X (cycle 1 only)	X	
Patient Diary g	X	X (every cycle)	X	
Concomitant medications	Continuous from time of ICF until 30 days of last treatment			
Adverse events	Continuous from time of ICF until 30 days of last treatment			
Study Drug Administration				
Daratumumab 1800 mg SC dosing h		Daratumumab 1800 mg SC on Days 1, 8, 15, and 22 of Cycles 1 and 2 (weekly dosing), on Days 1 and 15 of Cycles 3 to 6 (every 2 weeks dosing), and on Day 1 of Cycle 7 and subsequent cycles (every 4 weeks dosing)		

Clarithromycin		500 mg PO bid continuous days 1-28 of cycles 1-8 only		
Pomalidomide		Pomalidomide 4 mg PO days 1-21		

Dexamethasone		Dexamethasone (Cycle 1 D1 & 8): 20 mg IV Cycle 1 D2 & D9: 20mg PO Cycle 1 D15 & D22: 40mg PO Cycles 2- 6: 40 mg PO qwk Cycles 7- 8: 20mg PO qwk Cycle 9+: 20mg PO qwk		
Prophylactic Medications				
Varicella Zoster Prophylaxis		Valacyclovir 500mg PO qd (or equivalent, renally dosed-adjusted)		
Gastrointestinal Prophylaxis		Pantoprazole 40 mg PO daily, or other		
Laboratory Assessments				
Pregnancy test i	X	X	X	
Blood typing/indirect antiglobulin test	X			
Hematology (CBC) with differential	X	On Days 1, 8, 15, and 22 for Cycles 1 and 2; On Days 1 and 15 for Cycles 3 through 6; D1 from Cycle 7 onward and as clinically indicated	X	
Serum chemistry j	X	On Days 1, 8, 15, and 22 for Cycle 1-2, Day 1, 15 for cycles 3-6 and day 1 of each subsequent cycle	X	
Hepatitis B and C screening k	X	HBV DNA monitoring q12weeks	X	X i
Disease Assessments				
Serum $\beta$ 2-microglobulin	X			
Serum free light chains	X	X (every cycle)	X	X (every cycle)

SPEP and IFE	X	X (every cycle)	X	X (every cycle)
24-hour UPEP and IFE	X	X (every cycle)	X	X (every cycle)
PB/Urine for mass spec l		X l (only if $\geq$ VGPR achieved)		X l (every cycle)
Quantitative Immunoglobulins	X	X (every cycle)	X	X (every cycle)
NT-proBNP, BNP, Troponin T & I m	X	X (every cycle)	X	X (every cycle)
Skeletal survey or CT scan	X			
Bone marrow biopsy n,o	X	X n (to confirm CR only)	X n	
Correlative Studies				
BM aspirate for MFC and NGS o	X	X o (only if $\geq$ VGPR achieved)	X o	
PET/MRI p	X	X p (only if $\geq$ VGPR achieved)	X p	

- a. Patients must sign the informed consent form before any study-specific procedures are performed
- b. During Cycle 1, patients will have clinic visit with physical exam with physician or advanced practice provider on Day 8, 15, and 22.
- c. Vital signs include temperature, heart rate, blood pressure
- d. On daratumumab infusion days on Day 1 and 8 of Cycle 1, vital signs will be measured before, during, and after daratumumab infusions. For all other infusions, vital signs will be measured before the infusion start and at the end of the infusion.
- e. Only if history of respiratory disease or active symptoms. Must include measurement forced expiratory volume at one second (FEV1)
- f. Not required if PET or chest CT scan has been obtained
- g. Diaries will be provided to patients to record self-administered pomalidomide and dexamethasone dosed at home. At Screening, the patient will receive instructions on how to complete the diary and it will subsequently be reviewed at each visit to evaluate compliance with pomalidomide and dexamethasone.
- h. See section 6.2.1.3 for pre- and post- daratumumab infusion medications
- i. Pregnancy test will be performed in female patients of childbearing potential at the following timepoints: 10-14 days before the first dose on C1D1; 24 hours before the first dose on C1D1; weekly for first 4 weeks of C1; monthly thereafter beginning with C2; EOT visit (serum or urine  $\beta$ -hCG). Non-child-bearing potential is defined as female patients who are permanently sterile or are post-menopausal (no menses in 12 consecutive months without an alternative medical cause).
- j. Serum chemistries: Albumin, alkaline phosphatase, total bilirubin, bicarbonate, BUN, calcium, chloride, creatinine, glucose, LDH, phosphorus, potassium, total protein, SGOT [AST], SGPT [ALT], sodium.
- k. Hepatitis B screening includes hepatitis B core antibody (HBcAb) and hepatitis B surface antigen (HBsAg) and antibody (Anti-HBs) testing. If evidence of chronic HBV with positive anti-HBc or anti-HBs at screening, then must perform hepatitis B DNA test quantitative viral load q12w during treatment, at End of Treatment Visit, and q12w for up to 6 months after the last dose of study treatment. Hepatitis C screening includes hepatitis C antibody. If hepatitis C antibody reactive, then must perform hepatitis C RNA quantitative viral load.
- l. PB for mass spectrometry (MALDI-TOF MS), obtain at screening and day 1 of each cycle (only when in  $\geq$ VGPR), at EOT visits and D1 of each post-treatment observation phase cycle until PD or 24 months, whichever occurs first.
- m. If TTE is abnormal or clinical history of hypertension or heart disease
- n. Bone marrow assessment should include morphologic review, flow cytometry, conventional cytogenetics, and myeloma fluorescence in situ hybridization (FISH) panel. A repeat bone marrow biopsy may be performed if patient achieves a hematologic complete remission to assess for minimal residual disease.
- o. For research only: BM aspirate for correlative studies (3.3.1 - 3.3.3), obtain at screening and at best response (only if  $\geq$ VGPR achieved) and at 1 year: EDTA (DNA) and EDTA (MFC).
- p. For research only: PET/MRI for correlative studies (3.3.4), obtain at screening and at best response (only if  $\geq$ VGPR achieved) and at 1 year

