#### Cycles 9-30 Maintenance (28-day cycle)

- Daratumumab 1800 mg SC q4wks on Day 1
- Pomalidomide 4 mg PO on Days 1-21 of 28-day cycle
- Dexamethasone 20 mg PO will be administered as a premedication prior to daratumumab injection on day 1 of daratumumab.
- Dexamethasone 20 mg PO weekly on non-daratumumab treatment days

During the study, assessments will be performed as shown in the Study Calendar and as clinically indicated.

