**Table 6-2 Pomalidomide Dose Levels**

Dose Level	Dose (mg)
Starting Dose	4 mg
-1	3 mg
-2	2 mg
-3	1 mg

Table 6-3: Dose Modifications Guidelines for Pomalidomide:		
NCI CTC Toxicity Grade	Onset Day 2-14 of Cycle	Onset <math>\geq</math> Day 15 of Cycle
Grade 3 neutropenia associated with fever (temperature <math>\geq 38.5^{\circ}\text{C}</math>) or Grade 4 neutropenia	
 
• Hold (interrupt) pomalidomide.
 
• Follow CBC weekly.
 
• If neutropenia has resolved to <math>\leq</math> grade 2 prior to Day 21, restart at next lower dose level and continue through Day 21. If neutropenia is the only toxicity for which a dose reduction is required G-CSF may be used and the dose maintained
 
	
 
• Omit pomalidomide for remainder of cycle
 
• See Instructions for Initiation of a New Cycle (6.3.1) and reduce the dose by 1 dose level. If neutropenia is the only toxicity for which a dose reduction is required. G-CSF may be used and the dose maintained for the next cycle at the investigators discretion.
 

Thrombocytopenia <math>\geq</math> Grade 3 (platelet count <math>< 50,000/\text{mm}^3</math>)	
 
• Hold (interrupt) pomalidomide.
 
• Follow CBC weekly.
 
• If resolves to <math>\leq</math> grade 2 prior to Day 21, restart at next lower dose level and continue through Day 21.
 
	
 
• Omit pomalidomide for remainder of cycle
 
• See Instructions for Initiation of a New Cycle (6.3.1) and reduce the dose by 1 dose level.
 

Non-blistering rash Grade 3  Grade 4	
 
• If Grade 3, hold (interrupt) pomalidomide. Follow weekly.
 
• If the toxicity resolves to <math>\leq</math> grade 1 prior to Day 21, restart at next lower dose level and continue the cycle through Day 21.
 
• Discontinue and remove from study.
 
	
 
• Omit pomalidomide for remainder of cycle.
 
• See Instructions for Initiation of a New Cycle (6.3.1) and reduce the dose by 1 dose level.
 
• Discontinue pomalidomide. Remove patient from study.
 

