## Hematologic Toxicity

In trials 1 and 2 in patients who received pomalidomide + low-dose dex, neutropenia was the most frequently reported Grade 3/4 adverse reaction, followed by anemia and thrombocytopenia. Neutropenia of any grade was reported in 51% of patients in both trials. The rate of Grade 3/4 neutropenia was 46%. The rate of febrile neutropenia was 8%. Monitor patients for hematologic toxicities, especially neutropenia. Monitor complete blood counts weekly for the first 8 weeks and monthly thereafter. Patients may require dose interruption and/or modification

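### From cycle 7 the only scheduled blood count is on Day 1, after the pomalidomide-free week, so cytopenia reported by phase will tend to be understated more in maintenance than in induction

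*Combined protocol and SAP*

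**What the plan says.** **Calendar.** The haematology row of the Schedule of Study Procedures asks for counts "On Days 1, 8, 15, and 22 for Cycles 1 and 2", then "On Days 1 and 15 for Cycles 3 through 6; D1 from Cycle 7 onward and as clinically indicated". The visit window is plus or minus "7 days for Cycles 3-30".

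**Dosing.** Section 4.1 keeps the same pomalidomide pattern in maintenance as in induction: "Pomalidomide 4 mg PO on Days 1-21 of 28-day cycle". Days 22-28 are off drug.

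**Dose rules.** Table 6-3 (Section 6.3.3) sorts toxicity into two columns, "Onset Day 2-14 of Cycle" and onset on Day 15 or later. For neutropenia and thrombocytopenia the later column says "See Instructions for Initiation of a New Cycle (6.3.1) and reduce the dose by 1 dose level". Section 6.3.1 sets ANC and platelet thresholds for starting a cycle and a delay if they are not met.

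**Narrative monitoring text.** Section 6.7, Hematologic Toxicity: "Monitor complete blood counts weekly for the first 8 weeks and monthly thereafter".

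**Reporting.** The Protocol Summary lists "AEs in induction and maintenance phases" among the secondary objectives. Section 8.1.5 tabulates treatment-emergent events by worst grade per patient, with no split by phase and no account of how often blood was tested. Under Section 9.1.1 an abnormal laboratory value becomes an adverse event only if it leads to an action or is judged clinically significant.

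**The concern.** Worst observed grade can only stay the same or rise as more counts are taken. If one phase is sampled up to four times a cycle and the other once, at the end of a drug-free week, the two phases are not measured alike. Some short episodes in maintenance will begin and recover between two Day 1 counts. If they cause no symptoms, they produce no laboratory record and hence no adverse event.

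This bears on a main toxicity of the regimen. Section 1.3.2.2 reports Grade 3 or 4 neutropenia in 77% of 103 patients given daratumumab, pomalidomide and dexamethasone. A lower cytopenia rate in maintenance could be read as better tolerability when part of the difference is less testing. The primary endpoint and the 8-of-40 decision rule are not affected.

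There is also a gap in classification. Day 1 lies in neither onset column of Table 6-3, yet from cycle 7 it is the only scheduled count. The text does not say whether a cytopenia first found that day is a late onset from the previous cycle, with the dose reduction that column carries, or only a reason for delay under Section 6.3.1.

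**Working it through.** The plan states no figure on this point, so there is nothing to reproduce. The check has three steps.

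**1. Scheduled counts per patient** (calendar days; phases from Section 4.1)

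| Cycles | Count days | Counts | Days 2-14 | Day 15 or later |
|---|---|---|---|---|
| 1-2 | 1, 8, 15, 22 | 2 × 4 = 8 | 2 | 4 |
| 3-6 | 1, 15 | 4 × 2 = 8 | 0 | 4 |
| 7-8 | 1 | 2 × 1 = 2 | 0 | 0 |
| Induction total | | 18 | 2 | 8 |
| Maintenance | 1 | 22 or 24 | 0 | 0 |

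Induction: 18/8 = 2.25 counts per cycle, with 2 + 8 = 10 after Day 1. Maintenance: 1.00 per cycle, none after Day 1. Section 4.1 gives cycles 9-30 (22 cycles) and Section 7.4 gives 32 cycles in all (24 in maintenance); the per-cycle figure is the same. The earlier onset column loses its scheduled count at cycle 3 and the later column at cycle 7.

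**2. Does Section 6.7 conflict with the calendar?** Eight weeks is 56 days, or cycles 1-2, and both texts have weekly counts there. Afterwards Section 6.7 asks for monthly counts. The calendar gives two per 28 days in cycles 3-6 and one per 28 days from cycle 7. It meets or exceeds Section 6.7 throughout.

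**3. Direction and possible size (illustration only).** Assume an episode starts on day *o*, uniformly over a range of cycle days, and lasts *L* days. It is seen if a scheduled count day *d* satisfies *o* ≤ *d* < *o* + *L*, with the next Day 1 taken as day 29. With Day 1 counts only, this needs *o* ≥ 30 − *L*. For onset on Days 2-21 and *L* = 10, only days 20 and 21 qualify: 2/20 = 0.10. The induction average is (2 × weekly + 4 × two-weekly + 2 × Day 1 only)/8; for the same case, (2 × 1.00 + 4 × 0.60 + 2 × 0.10)/8 = 0.575, shown as 0.58.

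| Assumed length | Onset Days 2-21: induction / maintenance | Onset Days 2-28: induction / maintenance |
|---|---|---|
| 7 days | 0.42 / 0.00 | 0.55 / 0.22 |
| 10 days | 0.58 / 0.10 | 0.69 / 0.33 |
| 14 days | 0.82 / 0.30 | 0.87 / 0.48 |
| 21 days | 0.91 / 0.65 | 0.94 / 0.74 |

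Maintenance detection per episode is lower in every row, but the gap ranges from 0.20 (0.94 − 0.74) to 0.52 (0.82 − 0.30).

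Per patient, the longer maintenance phase pulls the other way. Take an assumed true episode probability of 0.10 per cycle in both phases, all 30 cycles completed and onset on Days 2-21. The true chance of at least one episode is 1 − 0.9^8 = 0.57 in induction and 1 − 0.9^22 = 0.90 in maintenance. With 14-day episodes the chance of seeing at least one is 1 − 0.9^2 × 0.9^4 × 0.97^2 = 0.50 in induction and 1 − 0.97^22 = 0.49 in maintenance. With 21-day episodes it is 1 − 0.9^6 × 0.935^2 = 0.54 and 1 − 0.935^22 = 0.77. So a per-patient worst-grade table need not show a lower figure in maintenance, but it falls further short of the truth there. This is why the comparison needs a patient-cycle denominator.

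**The case against.** The strongest reply is that safeguards exist and that no formal comparison is planned.

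- **Section 6.3.1 acts on the Day 1 count.** A cytopenia that persists to Day 1 delays the next cycle. This stands. It does not recover episodes that have resolved by then, and it does not say which Table 6-3 column applies.
- **Unscheduled counts are allowed.** The calendar permits clinically indicated counts, Section 6.7 allows additional testing, and fever in the Grade 3 neutropenia rule would itself prompt one. The seven-day window can also move a draw. A reader might infer that Table 6-3's cytopenia rules cannot be triggered from cycle 7. The documents do not support that. The table classifies toxicity by onset, however it is found, and Section 6.3 calls these provisions guidelines.
- **Section 6.7.** A reader might take it as a third, conflicting schedule. Step 2 of the working shows that it is not.
- **The by-phase comparison.** Only the synopsis names adverse events by phase; Sections 2.2 and 3.2 do not, and Section 8.1.5 is descriptive. This lowers the stakes, but meeting the synopsis objective still puts the two phases side by side.
- **The boundary.** Thinning starts at cycle 3 and reaches Day 1 only at cycle 7, both inside induction, so it does not coincide with the change of phase. The phase averages still differ, 2.25 against 1.00.
- **Other causes.** Maintenance patients are selected for PR or better, clarithromycin has stopped, and pomalidomide reductions are not reversed. Any of these could lower cytopenia genuinely, so a fall cannot be credited to testing alone.

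**Conclusion.** The concern holds as a point about unequal ascertainment. Scheduled counts fall from 2.25 per induction cycle to 1.00 per maintenance cycle, and from 10 counts after Day 1 to none. The count that remains nominally follows seven days without pomalidomide. Per cycle, laboratory Grade 3-4 cytopenia will tend to look less frequent in maintenance partly for that reason.

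The direction rests on the calendar at nominal days and assumes that unscheduled counts do not make up the difference. The size cannot be stated: the documents give no onset timing or episode length, and the detection figures above are illustrations under assumed values. The 77% quoted from the earlier daratumumab combination study carries no timing and does not size a maintenance effect.

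The remedy is a cheap improvement to safety reporting. The classification of a Day 1 finding is a separate matter of reconciling passages. Whether monitoring should be denser is a clinical question on which this review takes no position.

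**What to change.** **Analysis.** In Section 8.1.5, state that when cytopenia is reported by phase, two tables appear together:

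1. Grade 3-4 neutropenia and thrombocytopenia from all counts.
2. The same, per patient-cycle, from Day 1 counts only, which every cycle shares. Start at cycle 2, because the Cycle 1 Day 1 count precedes treatment.

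Build both from graded laboratory values rather than adverse event records, given the rule in Section 9.1.1. Print the number of counts per cycle, scheduled and unscheduled. State which phase is credited with the Cycle 9 Day 1 count, since it follows the last induction cycle.

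**Cost and limits.** One extra table from data already collected. The Day 1 table understates absolute nadir rates. It does not remove the selection of responders or the effect of earlier dose reductions. It supports a like-for-like comparison and nothing more.

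**Text.** Reconcile Table 6-3's onset columns with the calendar and Section 6.3.1, so that it is clear how a cytopenia first found on a Day 1 count is classified. This needs a short clarifying amendment. The schedule and the rule are for the clinicians to choose.
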